2.4 Protocol deviations

Frequency counts and percentages of patients in the FAS with any CSR-reportable protocol deviations (related to study inclusion/exclusion criteria, conduct of the trial, patient management or patient assessment) will be tabulated by the deviation category. All protocol deviations will be listed for the FAS.

The full list of potential CSR-reportable protocol deviations is documented separately in the Study Specification Document (SSD). All protocol deviations will be reviewed during the study and finalized before database lock.

2.5 Patient disposition

The FAS will be used for the patient disposition summary tables and listings. The following will be tabulated:

Treatment phase:

- Number (%) of patients who are still on-treatment (based on the absence of [End of Treatment Phase Disposition] eCRF page);
- Number (%) of patients who discontinued study treatment (based on the completion of [End of Treatment Phase Disposition] eCRF page with the 'Date of discontinuation' and 'Subject status (i.e., reason for discontinuation)' entered);
 - Number (%) of patients who entered post-treatment efficacy follow-up (based on the 'Next phase entered' is 'Post-treatment follow-up' (or 'Will the subject continue into the next phase of the trial?' is 'Yes') on the [End of Treatment Phase Disposition] eCRF page for patients who discontinued study treatment);
 - Number (%) of patients who entered survival follow-up (based on the 'Will the subject continue into the next phase of the trial?' is 'No' and 'Will the subject be followed for survival?' is 'Yes' on the [End of Treatment Phase Disposition] eCRF page for patients who discontinued study treatment);
 - Number (%) of patients who discontinued from study (based on the 'Will the subject continue into the next phase of the trial?' is 'No' and 'Will the subject be followed for survival?' is 'No' on the [End of Treatment Phase Disposition] eCRF page for patients who discontinued study treatment);
- Primary reasons for study treatment discontinuation (based on the 'Subject status (i.e., reason for discontinuation)' recorded on the [End of Treatment Phase Disposition] eCRF page for patients who discontinued study treatment);

Post-treatment efficacy follow-up phase:

- Number (%) of patients who are still in the post-treatment efficacy follow-up phase (based on the presence of [End of Treatment Phase Disposition] eCRF page and the absence of [End of Post Treatment Phase Disposition] eCRF page for patients who entered post-treatment efficacy follow-up);
- Number (%) of patients who discontinued from the post-treatment efficacy follow-up (based on the completion of [End of Post Treatment Phase Disposition] eCRF page with the 'Date of discontinuation' and 'Subject status (i.e., reason for discontinuation)' entered for patients who entered post-treatment efficacy follow-up);
 - Number (%) of patients who entered survival follow-up (based on the 'Will the subject be followed for survival?' is 'Yes' on the [End of Post Treatment Phase Disposition] eCRF page for patients who discontinued from the post-treatment efficacy follow-up);

- Number (%) of patients who discontinued from study (based on the 'Will the subject be followed for survival?' is 'No' on the [End of Post Treatment Phase Disposition] eCRF page for patients who discontinued from the post-treatment efficacy follow-up);
- Primary reasons for discontinuation from the post-treatment efficacy follow-up (based on the 'Subject status (i.e., reason for discontinuation)' recorded on the [End of Post Treatment Phase Disposition] eCRF page).

The patient disposition will be listed for the FAS. The informed consent data will be listed for the screen failures as well as the FAS.

2.6 Treatments (study drug, concomitant therapies, compliance)

The Safety Set will be used for all medication data summaries and listings unless otherwise specified.

Study drug and study treatment

Study drug and study treatment both refer to LDK378 and will be used interchangeably.

Date of first/last administration of study drug

The date of first administration of study drug is defined as the first date when a non-zero dose of study drug was administered and recorded on the [Dosage Administration Record (DAR)] eCRF page. For the sake of simplicity, the date of first administration of study drug will also be referred to as start date of study drug.

The date of last administration of study drug is defined as the last date when a non-zero dose of study drug was administered and recorded on the DAR eCRF page. This date will also be referred to as last date of study drug.

Study day

The study day for all assessments (e.g., tumor assessment, death, disease progression, tumor response, performance status, adverse event onset, laboratory abnormality occurrence, vital sign measurement, and dose interruption) will be calculated using the start date of study drug as the origin. For assessments occurring after or on the start date of study drug, study day will be calculated as:

Study day = Event date – Start date of study drug + 1.

The first day of study drug is therefore study day 1.

For any assessment or events such as baseline disease characteristics or medical history (e.g., time since diagnosis of disease) occurring prior to the start of the study drug, study day will be negative and will be calculated as:

Study day = Event date – Start date of study drug.

The study day will be displayed in the relevant data listings.

Dose exposure and intensity

Definitions of study drug exposure variables, as well as intermediate calculations, are provided in [Table 2-1](#).

Table 2-1 Study drug exposure variables

Variable	Definition
Duration of exposure (days):	Last date of study drug – Start date of study drug + 1 (Periods of interruption are not excluded.)
Cumulative dose (mg):	Total dose of study drug taken by a patient in the study
Number of dosing days (days):	Duration of exposure (days) – Number of zero dose days
% of actual days dosed (%):	$100 \times \text{Number of dosing days} / \text{Duration of exposure (days)}$
% of days received full dose (%):	$100 \times \text{Number of days received full (planned) dose} / \text{Duration of exposure (days)}$
Average daily dose (mg/day):	$\text{Cumulative dose (mg)} / \text{Number of dosing days}$
Dose intensity; DI (mg/day):	$\text{Cumulative dose (mg)} / \text{Duration of exposure (days)}$
Relative dose intensity; RDI (%):	$100 \times \text{DI (mg/day)} / \text{Planned dose (i.e., 750 mg/day)}$

Note:

Given the planned dose of 750 mg/day, the planned dose intensity (PDI) can be calculated as:

$\text{PDI (mg/day)} = \text{Cumulative planned dose (mg)} / \text{Duration of exposure (days)}$,

where

$\text{Cumulative planned dose (mg)} = \text{Planned dose of 750 (mg)} \times \text{Duration of exposure (days)}$.

Then, RDI (%) which is calculated as $(100 \times \text{DI} / \text{PDI})$ can be simplified as shown above.

Duration of exposure to study drug, cumulative dose, average daily dose, DI and RDI will be summarized. In addition, the duration of exposure to study drug and RDI will be categorized and the frequency counts and percentages of patients in each category will also be presented.

Frequency counts and percentages of patients who have dose changes, reductions or interruptions, and the corresponding reasons, will be summarized. In addition, descriptive statistics will also be presented for the % of actual days dosed, % of days received full dose, number of dose changes, and number of dose interruptions.

Time to first dose reduction, defined as the time from the first dose of study drug to the first reduction of study drug, will be summarized in 2 month-intervals. Summary statistics of time to first dose reduction will also be presented. Time to first dose interruption, defined as the time from the first dose of study drug to the first interruption of study drug, will be summarized in a similar way.

Listings of all doses of the study drug along with dose change and dose interruption reasons will be produced. The derived exposure variables will also be listed by patient.

[Section 4.6](#) provides further details on the definition of dose changes and interruptions.

Concomitant therapy

Concomitant therapies are defined as any medications (excluding study drug, prior antineoplastic treatments and blood transfusions), surgeries or procedures (including physical

therapy) administered in the study and are recorded in the [Prior and Concomitant Medications] and the [Surgical and Medical Procedures] eCRF pages, respectively.

Concomitant medications will be coded using the WHO Drug Reference List (WHO DRL) dictionary that employs the WHO Anatomical Therapeutic Chemical (WHO ATC) classification system. Surgeries or procedures will be coded using the MedDRA terminology.

All summaries will be tabulated using frequency counts and percentages. Concomitant medications will be summarized by ATC class and preferred term. These summaries will include: 1) medications starting on or after the start of study drug and starting no later than 30 days after last dose of study drug and 2) medications starting prior to the start of study drug and continuing after the start of study drug. Surgeries or procedures will be summarized by primary system organ class and preferred term in a similar way.

All concomitant therapies will be listed. Any concomitant therapies starting and ending prior to the start date of study drug or starting more than 30 days after the last date of study drug will be flagged in the listings.

Note patients who receive the prohibited concomitant therapies will be reported as a protocol deviation.

Antineoplastic therapy after discontinuation of study drug

The FAS will be used for all listings and summaries of antineoplastic therapies initiated after discontinuation of study drug.

Antineoplastic therapies initiated after discontinuation of study drug will be listed in three separate categories: (i) medications, (ii) radiotherapy, and (iii) surgery.

All summaries will be tabulated using frequency counts and percentages. Antineoplastic medications initiated after discontinuation of study drug will be summarized by ATC class and preferred term.

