1.2.1.2 Clinical experience

1.2.1.2.1 Clinical safety and tolerability

LDK378 is generally associated with a manageable safety profile.

In CLDK378X2101, as of the 14-April-2014 cut-off date, total of 255 ALK positive patients were enrolled 246 NSCLC (98.4%) and 9 Non-NSCLC (3.6%). For the 246 patients with ALK positive NSCLC treated at the recommended dose of 750 mg in this ongoing study, the median duration of exposure was 38.6 weeks (range 0.4 to 105.9). At least one dose reductions due to adverse events occurred in 61.8% of patients treated with LDK378 at the 750 mg dose. In 255 ALK positive patients, the most common adverse events regardless of study drug relationship (incidence $\geq 25\%$) were diarrhea, nausea, vomiting, alanine aminotransferase (ALT) increased, fatigue, abdominal pain, decreased appetite, aspartate aminotransferase (AST) increased, constipation, and cough. The frequently occurred grade 3-4 Adverse events (AEs) ($>5\%$), regardless of study drug relationship were ALT (Alanine aminotransferase) increased (29.8%), AST increased (9.8%), lipase increased (6.3%), diarrhea (5.9%), nausea (5.9%), hyperglycemia (5.9%), fatigue (5.1%), anaemia (5.1%) and blood alkaline phosphatase increased (5.1%) ([Table 1-1](#)).

Table 1-1 All grades (at least 10%) and grade 3-4 adverse events, regardless of study drug relationship, by preferred term in patients treated in the 750 mg dose group (Safety Set) (Data cut-off: 14-April-2014)

Preferred term	LDK378 750 mg N=255	
	All Grades n (%)	Grade 3/4 n (%)
Total	255 (100.0)	206 (80.8)
Diarrhea	221 (86.7)	15 (5.9)
Nausea	211 (82.7)	15 (5.9)
Vomiting	157 (61.6)	12 (4.7)
Alanine Aminotransferase Increased	112 (43.9)	76 (29.8)
Fatigue	109 (42.7)	13 (5.1)
Abdominal Pain	98 (38.4)	3 (1.2)
Decreased Appetite	95 (37.3)	4 (1.6)
Aspartate Aminotransferase Increased	83 (32.5)	25 (9.8)
Constipation	79 (31.0)	0
Cough	73 (28.6)	0
Dyspnea	63 (24.7)	11 (4.3)
Abdominal Pain Upper	60 (23.5)	2 (0.8)
Asthenia	50 (19.6)	2 (0.8)
Back Pain	50 (19.6)	1 (0.4)
Headache	51 (20.0)	4 (1.6)
Weight Decreased	46 (18.0)	5 (2.0)
Blood Alkaline Phosphatase Increased	45 (17.6)	13 (5.1)
Blood Creatinine Increased	43 (16.9)	0
Pyrexia	42 (16.5)	0
Insomnia	39 (15.3)	0
Musculoskeletal Pain	37 (14.5)	0
Rash	34 (13.3)	0
Dyspepsia	32 (12.5)	1 (0.4)
Anemia	31 (12.2)	13 (5.1)
Dizziness	31 (12.2)	0
Hypokalemia	29 (11.4)	11 (4.3)
Edema Peripheral	27 (10.6)	0
Musculoskeletal Chest Pain	27 (10.6)	0
Non-Cardiac Chest Pain	26 (10.2)	2 (0.8)

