Arthralgia	26 (10.2)	0

The most frequent AEs requiring dose adjustments or interruptions reported in $\geq 5\%$ of the patients were: ALT increased, nausea, diarrhea, AST increased, vomiting, fatigue, abdominal pain, decreased appetite and lipase increased. AEs leading to study drug discontinuations occurred in 10.2% of patients treated with LDK378 at the 750 mg dose. The most frequent AEs (which occurred in two or more patients) leading to study drug discontinuations were

pneumonia, ALP increased, decreased appetite, general physical health deterioration, pneumonitis, and respiratory failure

Serious adverse events (SAEs) reported in 47.5 % of the 255 patients treated at the recommended dose of 750 mg were pneumonia, interstitial lung disease (ILD)/pneumonitis, convulsion, dyspnea, nausea, hyperglycemia, pericardial effusion and respiratory failure (incidence $\geq 2\%$). On treatment death except death due to the cancer occurred in 14 patients, consisting of: pneumonia and respiratory failure in 3 patients and acute respiratory failure, cardiac tamponade, gastric haemorrhage, ILD, pneumothorax, pulmonary tuberculosis, respiratory failure sepsis and septic shock (1 patient each). Adverse events of special interest to be monitored for LDK378 have also been identified and include: hepatotoxicity, interstitial lung disease/pneumonitis, QT interval prolongation, bradycardia, hyperglycemia, gastrointestinal toxicity (nausea, vomiting and diarrhea), and pancreatitis (including lipase and amylase elevations). For additional details, refer to [Investigator's Brochure].

In Japanese phase I study with expansion phase, CLDK378X1101, total of 20 patients with ALK-rearranged tumor patients, 19 (95%) with NSCLC and 1 (5%) inflammatory myofibroblastic tumor were enrolled as of the 4-Jul-2014 cut-off date. The median duration of exposure was 32.1 weeks (range 0.1 to 86.7). In dose escalation phase, tolerability up to 750 mg/day was confirmed. All patients experienced ≥ 1 AE regardless of study drug relationship. The most common AEs were nausea (95%), diarrhea (75%) and vomiting (75%). Grade 3 or 4 AEs regardless of study drug relationship were reported in 16 patients. The most frequent grade 3 or 4 AEs were ALT increased and tumor pain, each of which occurred in two patients (10%) ([Murakami et al 2014](#)).

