10.5.3.5 Tolerability

Tolerability will be evaluated in terms of dose reductions or drug interruptions due to an AE.

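### Time to first dose reduction and time to first interruption have no rule for patients without the event, so the planned mean and median describe only patients with an observed event and are biased short for treated patients

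*SAP*

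**What the plan says.** SAP 2.6, under dose exposure and intensity, gives the definition "Time to first dose reduction, defined as the time from the first dose of study drug to the first reduction of study drug". It asks for this time in 2-month intervals and adds: "Summary statistics of time to first dose reduction will also be presented". For interruptions the definition runs from first dose to first interruption, and the variable "will be summarized in a similar way".

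The same section makes the Safety Set the default population for medication summaries. SAP 2.1 says that continuous data are described by mean, standard deviation, median, minimum and maximum.

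No rule covers patients without the event. SAP 4.6 defines and counts interruptions and dose changes but says nothing about these times. SAP 4.7.4, within the efficacy section, sets out Kaplan-Meier for DOR, PFS and OS. Protocol 10.3 asks for dose reductions and delays to be listed and summarised and does not mention these times.

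On why the variables matter, Protocol 10.5.3.5 states: "Tolerability will be evaluated in terms of dose reductions or drug interruptions due to an AE". On how common reductions were in the earlier 750 mg experience, Protocol 1.2.1.2.1 states: "At least one dose reductions due to adverse events occurred in 61.8% of patients treated with LDK378 at the 750 mg dose".

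**The concern.** Both variables are times to an event that some patients will not have. Three kinds of patient have no value under the definition: those who stop LDK378 without a reduction (progression, adverse event, death or another reason), those still on the starting dose at the cut-off, and the corresponding two groups for interruptions. A mean or median needs a number for each patient counted, so a programmer following the SAP literally would drop these patients.

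The resulting median answers how early the event came among those who had it. A reader of the clinical study report is likely to take it as the time by which half of treated patients had been reduced, which is a different and later time. The events-only figure also depends on how long patients have been followed. Two reports are planned, at different cut-offs, so the value can shift between them although the rate of reductions has not changed.

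Elsewhere the SAP is explicit. TTR is limited to confirmed responders, and DOR, PFS and OS have censoring rules. These two times have neither.

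**Working it through.** **Inputs**
- Share with a reduction for adverse events: p = 61.8% (Protocol 1.2.1.2.1, earlier study at 750 mg). Check: 152/246 = 61.79%, which rounds to 61.8%; no whole number out of 255 does. Complement: 38.2%, or 0.382 × 20 = 7.6 of 20 patients.
- Median exposure in that study: 38.6 weeks, used as an assumed median time to stopping drug. Sensitivity values: 32.1 weeks (Japanese phase I study, same section) and 60 weeks (my assumption).
- Primary cut-off: about 168 days, or 24 weeks, after the last patient's first dose (SAP 2.1).
- Assumed: constant hazards for first reduction (h) and for stopping without one (d), with h/(h + d) = p.

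**Hazards at 38.6 weeks**
- d = ln 2/38.6 = 0.01796 per week
- h = d × 0.618/0.382 = 0.02905 per week
- h + d = 0.04701 per week

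**Three medians for the same data**
- Among patients with a reduction: ln 2/(h + d) = 14.7 weeks.
- Kaplan-Meier, censoring at stopping: ln 2/h = 23.9 weeks.
- Cumulative incidence reaching 50% of all treated patients, stopping as competing: −ln(1 − 0.5/0.618)/(h + d) = 1.656/0.04701 = 35.2 weeks.

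The events-only median is 62% of the Kaplan-Meier value and 42% of the cumulative-incidence value.

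| Median time to stopping | Events only | Kaplan-Meier | Cumulative incidence |
|---|---|---|---|
| 32.1 weeks | 12.3 | 19.8 | 29.3 |
| 38.6 weeks | 14.7 | 23.9 | 35.2 |
| 60 weeks | 22.9 | 37.1 | 54.8 |

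**Direction.** If F(t) is the cumulative incidence and p its final level, the events-only distribution is F(t)/p. Since p is below 1, F(t)/p is never less than F(t), so its median cannot exceed the all-patient median, whatever the shape of F. The all-patient median is the 0.5/0.618 = 80.9th percentile of the observed event times. With Weibull event times of shape 2 to 0.5, the ratio of the two medians runs from 1.5 to 5.7; it is 2.4 for the exponential.

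**Dependence on follow-up.** With a cut at week c, the events-only distribution is F(t)/F(c), so the median rises with c.
- Every patient cut at 24 weeks: F(24) = 0.618 × (1 − exp(−0.04701 × 24)) = 41.8%, events-only median 8.8 weeks. This is a lower extreme, because 24 weeks is the minimum follow-up, for the last patient only.
- Staggered entry, assuming 20 patients at one per month, so that follow-up is 24, 28.3, 32.7 weeks and so on. Setting the summed F(min(t, c)) over patients equal to half the summed F(c) gives 13.0 weeks. At two per month it gives 11.9 weeks.
- Unlimited follow-up: 14.7 weeks.

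**Interruptions.** The documents give no share. If 55% to 90% of patients have one, the same model puts the events-only median at 55% to 90% of the Kaplan-Meier median and at 29% to 85% of the cumulative-incidence median.

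**The case against.** The strongest reply is that the SAP never says these summaries are restricted to patients with the event. The default population is the Safety Set, and where the SAP wants a restriction, as for TTR, it states one. This is correct as a reading of the text, but it does not remove the problem: the definition gives no number for a patient without the event, so the mean and median cannot be taken over the whole Safety Set.

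A second reply is that much of the remedy is already planned. SAP 2.6 asks for 2-month intervals and for counts and percentages of patients with reductions or interruptions. If the interval table uses the Safety Set denominator, adding up its rows gives the crude proportion with a first event. Nobody still on drug is cut off before 168 days, which is 168/30.4375 = 5.5 months, so at 2 and 4 months the crude proportion equals the competing-risks estimate. This stands and limits the risk of misreading. It does not reach the mean and median, or the intervals beyond 5.5 months.

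A third reply concerns importance. Neither time is a listed endpoint or is requested in Protocol 10.3, both count events for any reason, and adverse-event-driven changes have their own tables. This also stands, and it keeps the point small. SAP 4.7.4 sits under efficacy and would not be expected to cover exposure variables, so its silence is not an error in that section.

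The inputs are borrowed as well. The earlier study was ongoing, and 83 of its 246 NSCLC patients were ALK-inhibitor naive. The 61.8% is a share at a data cut, treated here as a final one.

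**Conclusion.** The gap is real and the direction of the bias is certain against cumulative incidence; the amount is not. Under constant hazards with the earlier study's figures, the events-only median of 14.7 weeks compares with 23.9 weeks by Kaplan-Meier and 35.2 weeks by cumulative incidence. These are different quantities, so the gaps measure how far a reader could be misled; they are not errors in a stated result.

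Three stronger readings are tempting and not supported.
- A reader might apply the 38% without the event to both variables. It covers reductions due to adverse events in another study. For interruptions no share is given, and if most patients interrupt, the bias is small.
- A reader might conclude that the statistics must come out far too short. That depends on the event-time shape and on the target.
- A reader might take 8.8 weeks as the expected value at the primary analysis. That cuts every patient at 24 weeks; with one or two patients entering per month the figure is about 13.0 or 11.9 weeks, so the expected shift between reports is modest under these hazards.

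This is a small, cheap improvement to a descriptive exposure summary. It has no bearing on ORR or on any decision rule.

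**What to change.** In SAP 2.6, replace the plain statistics for both variables with the cumulative incidence of first dose reduction and of first interruption on the whole Safety Set, at 2, 4, 6 months and so on. Treat permanent discontinuation of LDK378 or death without the event as a competing event, and censor patients still on drug without the event at the analysis cut-off.

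If the mean and median are kept, label them *among patients with the event (n/N)*, state that the 2-month table uses the Safety Set denominator, and add a *no event* row to it.

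Cost: a few lines of SAP text and one extra descriptive table by a standard method (Aalen-Johansen). The dosing, disposition and death dates needed are already collected.
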